3. STUDY DESIGN

3.1 Description of the Study

This is a prospective *between and within group* observational study to determine differences in tolerability, immunogenicity and safety related outcomes for MS patients who have been administered at least two infusions of rituximab, with the last dose of rituximab within 12 months of screening and are willing to be switched to ocrelizumab, compared to patients who are continuing on rituximab as a comparison cohort from the clinic population treated as part of routine clinical care in our program.

The comparator arm is an observational arm only. In addition to prospective data collection, we will collect infusion-related reaction data retrospectively for infusions done after August 1, 2016 (when we began collecting infusion reactions in a standardized way as part of standard of care at the infusion center).

Retrospective data will be collected only after consent is obtained.

In a prospective evaluation with patients at RMMSC who are currently on sustained rituximab treatment for their MS, we will examine the frequency and

severity of IRRs for 100 patients who switch to ocrelizumab (**switching group**) compared to 200 patients continuing rituximab as our primary outcome (**comparator group**). Our secondary outcome is to examine anti-drug antibody formation post switching from rituximab to ocrelizumab (**switching group**). Comparisons for the both outcomes will also be made to findings from the OPERA I and II randomized clinical trials. Other exploratory outcomes including the measurement of B cell reconstitution, cytokine reactions and adverse event profiles will also be examined.

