3.3 Outcome Measures

3.3.1. Primary Outcome Measure

Primary endpoint:

- a. Primary endpoint: The primary end point will be proportion of infusions with ≥ 1 IRR between the switching and comparator groups.
- b. Secondary IRR assessments:
 - a. We will also report the difference in the total number of IRRs after each infusion of ocrelizumab in the switching group compared to similar rituximab infusions in the comparator group.
 - b. The difference in proportion of patients with ≥ 1 IRR across any of their infusions between the switching and comparator groups
 - c. We will also compare the proportion of patients with an IRR following day 1 infusion versus the proportion of patients with an IRR at day 15 and month 6 infusions of ocrelizumab in the switching group.
 - d. The severity of IRRs will be assessed following each infusion of ocrelizumab in the switching and comparator group using the National Cancer Institute's Common Terminology for Adverse Events Scale.⁶ The frequency of each severity grade of IRR will be compared in a similar fashion.

Nursing staff at the University of Colorado's Outpatient Infusion Center will be responsible for classifying the severity of an IRR for each patient at the end of every ocrelizumab and rituximab infusion using the scale below. Nursing staff will be asked to record the highest grade of an IRR that they observed or intervened upon for each patient after completion of their infusion.

Severity of IRR:

Grade 0: No infusion reaction

Grade 1: Mild reaction (transient flushing or rash drug fever < 38 degrees C); infusion interruption not indicated; intervention not indicated

Grade 2: Requires therapy or infusion interruption but responds promptly to symptomatic treatment (e.g., antihistamines, NSAIDs, narcotics); prophylactic medications indicated for 24 hours.

Grade 3: Prolonged (i.e., not rapidly responsive to symptomatic medication and/or brief interruption of infusion); recurrence of symptoms following initial improvement; hospitalization indicated for other clinical sequelae (e.g., renal impairment, pulmonary infiltrates)

Grade 4: Life threatening consequences; urgent intervention indicated.

Grade 5: Death

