Potential study patients will be identified from RMMSC electronic medical records (EPIC) using the study inclusion and exclusion criteria. Patients will be recruited by the study coordinator through the University of Colorado's Outpatient Infusion Center. Potential patients are already being identified through their MS providers at RMMSC with whom discussions about the possibility of switching to ocrelizumab are currently underway. Study participants who complete the observation phase of the study will be offered the ability to continue to receive ocrelizumab infusions provided for free by Genentech until ocrelizumab is approved and available to them through their health insurance plan. Once ocrelizumab is available by prescription they will receive priority for assistance through the Genentech/Roche Patient Assistance Program for Ocrelizumab for out of pocket expenses. Ocrelizumab will be provided through priority placement in Genentech's patient assistance program for those patients who are not able to receive insurance coverage for it.

MS patients included in this study will have made a decision with their provider to either stay on rituximab or to switch to ocrelizumab outside of this study. The decision to switch to ocrelizumab or to stay on rituximab will be made as part of

the clinical treatment process between the patient and his/her provider based on his/her disease severity and suitability for treatment among other factors. Therefore, patients are not randomized into either treatment arm. For the group that stays on rituximab, participation in this study is purely observational. For those patients in the rituximab arm who are deemed to be appropriate candidates for switching to ocrelizumab, the option to do so will be provided as standard of care under priority access and/or patient assistance programs (contingent on their individual health insurance status).

It is important to note that because the incidence of IRRs for infusions prior to enrollment are not collected prospectively for those continuing treatment with rituximab and because adverse events including IRRs will not be collected using the same methods for each treatment group following enrollment, interpretation of any difference in the incidence of these events will be limited.

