After completion of the infusion, the IV cannula should remain in situ for at least 1 hour to allow for administration of drugs intravenously, if necessary, in the event of a delayed reaction. If no adverse events occur during this period of time, the IV cannula may be removed and the patient may be discharged. See the Ocrelizumab Investigator's Brochure for detailed instructions on drug preparation, storage, and administration.

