4.5.1 Assessments during Treatment

The following evaluations will be conducted during and post treatment:

Study Visits and Procedures Summary:

Study visits for the switching group include a) screening visit, b) first infusion of 300 mg of ocrelizumab (day 1 or T₀), c) 300 mg of ocrelizumab infusion on day 15 (T₁), d) 600 mg of ocrelizumab at 6 months (+/- 2 weeks) after day 1 (T₂) and, e) a research termination visit between month 12 and 18 - (+/- 2 weeks)(T₃). In some cases, screening procedures may be performed on the first infusion day rather than as a separate visit. The patient may continue on 600 mg of ocrelizumab or (if the patient prefers) 500mg rituximab at T₃, or 12 to 18 months after Day 1 (T₀). A month is defined as 28 days. Study visits for the comparator group include only standard of care infusion of rituximab, up to two infusions per patient, approximately 6 months apart. Research data on IRRs for the comparator group will be collected from the medical records.

A summary of all procedures for switching group is outlined under “Schedule of Events” in **Table 1** below. During the screening visit, patients will be consented for the study and receive both a medical and full neurological exam. Verification of their hepatitis B and C status including testing will be conducted if a patient has not been tested in the last two years. MS disease history and demographic information will also be collected. Patients will also receive an EDSS exam and take an online version of the PDDS (done as standard of care- on an iPad).

The Expanded Disability Status Scale (EDSS) is a commonly used assessment that allows clinicians to objectively measure changes in the disability status of MS patients using unbiased clinical raters.⁷ The **EDSS** provides a total score on a scale that ranges from 0 to 10. The first levels 1.0 to 4.5 refer to people with a high degree of ambulatory ability and the subsequent levels 5.0 to 9.5 refer to the loss of ambulatory ability. The range of main categories include (0) = *normal neurologic exam*; to (5) = *ambulatory without aid or rest for 200 meters; disability severe enough to impair full daily activities*; to (10) = *death due to MS*. In addition, it also provides seven subscale measurements called Functional System (FS) scores.

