4.9.6 Determination of Sample Size

The sample size will be a convenience sample. It is anticipated a minimum of 100 patients will qualify for each cohort (200 total) resulting in studying 300 infusions with ocrelizumab and 200 infusions with rituximab. This is an observational study not designed to demonstrate superiority of ocrelizumab over rituximab in efficacy but instead indicate the magnitude of the relative tolerability and immunogenicity. The primary endpoint is the difference in the percentage of IRRs between the two study groups. In addition, both study groups will include treatment experienced patients on rituximab who have experienced a minimum of two infusions and either continue to stay on rituximab or switch to ocrelizumab.

To estimate study power with the proposed sample size of 100 infusions in each group, we conducted a chart review of 50 patients at the Rocky Mountain MS Center who are currently taking rituximab and examined their IRRs using the proposed IRR grading scale (see section 3.3.1) from Grade 0-5. The number and severity of IRRs were captured following their third rituximab infusion. The highest grade of an IRR that occurred during the infusion was recorded. Our pilot data revealed that following the third rituximab infusion, 14.3% of patients had an IRR of which 85.71% were Grade 0, 12.24% were grade 2 and 2.05% were Grade 3. Hauser et al., found that following the second infusion of rituximab in patients, the majority of whom (60%) were not taking a DMT for 6 months prior to initiating rituximab only 20.3% experienced in an IRR.³

Using IRR estimates from our pilot data and establishing a clinically meaningful difference of 20% increase in IRRs, we conducted the following power analysis for a sample of 95 patients (assuming a 5% attrition rate after recruiting 100 patients in each study group). An IRR proportion for ocrelizumab users at 34.3% compared with 14.3% for rituximab (obtained from our pilot data) for a two sided (alpha = 0.05) two sample proportion test for the null hypothesis of no difference between rituximab and ocrelizumab in proportion of IRRs would result in 90% power for 95 patients per group.

In response to the FDA IND letter, “the power analysis in Section 4.9.6 of the protocol appears to compare the infusion-related reaction (IRR) rate at the third rituximab infusion (14.3%) to that of the first infusion of OCR (34.3%). Because

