5.2 Methods and Timing for Assessing and Recording Safety Variables

The investigator is responsible for ensuring that all AEs and SAEs that are observed or reported during the study, are collected and reported to the FDA, appropriate IRB(s), and Genentech, Inc. in accordance with CFR 312.32 (IND Safety Reports).

Adverse Event Reporting Period

The study period during which all AEs and SAEs must be reported begins after informed consent is obtained and initiation of study treatment or "initiation of any study procedures" and ends at T₃ which is 6 months after last dose of study medication. After this period, investigators should only report SAEs that are attributed to prior study treatment.

Assessment of Adverse Events

AEs and SAEs may be collected from medical record review, or elicited by asking non-directive questions at each study visit both before and after the infusion. Infusion-related AEs will be captured by the infusion nurses as well as self-reported by the patient as described in Outcome Measures. Patients will also be reminded to alert the study team about any concerning health issues between study visits. Each recorded AE or SAE will be described by its duration (i.e., start and end dates) and will include, and actions taken.

For all recorded AEs, a study investigator will make an assessment of seriousness, and causality. To ensure consistency of AE and SAE causality assessments, investigators should apply the following general guideline:

Yes

There is a plausible temporal relationship between the onset of the AE and administration of the ocrelizumab, and the AE cannot be readily explained by the subject's clinical state, intercurrent illness, or concomitant therapies; and/or the AE follows a known pattern of response to the ocrelizumab; and/or the AE abates or resolves upon discontinuation of the ocrelizumab or dose reduction and, if applicable, reappears upon re-challenge.

No

Evidence exists that the AE has an etiology other than the ocrelizumab (e.g., preexisting medical condition, underlying disease, intercurrent illness, or concomitant medication); and/or the AE has no plausible temporal relationship to ocrelizumab administration (e.g., event diagnosed 2 days after first dose of ocrelizumab).

Expected adverse events are those adverse events that are listed or characterized in the Package Insert or current Investigator Brochure.

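### The protocol does not settle whether the primary endpoint, infusion-related reactions, is ascertained the same way in both groups, and no planned analysis covers unequal ascertainment

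*Combined protocol and SAP*

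**What the plan says.** Section 3.3.1 sets the endpoint: "The primary end point will be proportion of infusions with ≥ 1 IRR between the switching and comparator groups". The same section makes infusion-centre nurses responsible for grading reactions from 0 to 5 after every infusion of either drug. Section 4.5.1 repeats that nurses record reactions after each rituximab infusion, as standard care.

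Section 4.2 says something different: "adverse events including IRRs will not be collected using the same methods for each treatment group following enrollment". It concludes that "interpretation of any difference in the incidence of these events will be limited".

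For the comparator group, section 4.5.1 states: "Research data on IRRs for the comparator group will be collected from the medical records". Section 3.1 adds that "we will collect infusion-related reaction data retrospectively for infusions done after August 1, 2016", the date from which the infusion centre recorded reactions in a standardised way.

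The switching group has further channels. Section 5.2 states: "Infusion-related AEs will be captured by the infusion nurses as well as self-reported by the patient as described in Outcome Measures". It also provides for adverse-event questions before and after the infusion at study visits. Table 1 schedules self-report of IRRs at each ocrelizumab infusion, and section 3.4 adds a coordinator interview at each visit. The comparator group has only its standard-care infusions.

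Section 4.9.4 plans one sensitivity analysis, comparing unadjusted with covariate-adjusted results to gauge confounding.

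**The concern.** Any reaction of Grade 1 or higher makes an infusion an event, so the endpoint depends on how completely mild reactions are noticed and written down. If that completeness differs by group, the estimated difference mixes a drug effect with a recording effect. A larger sample does not remove the bias, and neither do the matching, regression and propensity methods in sections 4.2 and 4.9.4, because they address who is in each group and not how the outcome is measured.

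Sections 3.3.1 and 4.2 cannot both be a full description of the primary endpoint. Either the nurse's grade is the sole source in both groups, and section 4.2 overstates the problem, or something else enters in one group and the plan does not say what. All the additional prompts the documents describe are on the ocrelizumab side, so if there is a bias it plausibly runs toward more IRRs on ocrelizumab.

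**Working it through.** **Step 1. The plan's own figure.** Section 4.9.6 gives 34.3% v 14.3%, two-sided alpha 0.05, 95 per group and 90% power.

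Formula: power = Φ[(d − 1.96·SE0)/SE1], where SE0 uses the pooled rate and SE1 the separate rates.

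- d = 0.200 and pooled rate = 0.243
- SE0 = √(0.243 × 0.757 × 2/95) = 0.0622
- SE1 = √(0.143 × 0.857/95 + 0.343 × 0.657/95) = 0.0605
- (0.200 − 1.96 × 0.0622)/0.0605 = 1.29, so power = 0.901

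The 90% reproduces. The calculation takes recording to be equally complete in both groups.

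**Step 2. What unequal recording would do.** The documents give no capture rate, so this step is hypothetical.

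- True rate p, the same in both groups: 14.3% (the pilot rate in section 4.9.6) or 20.3% (the second rituximab infusion in the phase 2 trial, section 1).
- Capture in switchers: 100% (assumed).
- Capture in the comparator, s: 80% or 70% (assumed).
- Infusions: 300 v 200 (section 4.9.6), or 95 v 95 as in the power calculation.

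False excess = p × (1 − s). The false-positive rate is the two-sided rejection probability from the Step 1 formula, with observed rates p and s·p.

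Example with p = 20.3%, s = 70%, 300 v 200:

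- d = 0.203 − 0.142 = 0.061 and pooled rate = 0.179
- SE0 = 0.0350 and SE1 = 0.0339
- (0.0609 − 1.96 × 0.0350)/0.0339 ≈ −0.23, so the rejection probability is 0.41

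For within-patient correlation, an intraclass correlation (ICC) of 0.3 is assumed, with three ocrelizumab and two rituximab infusions per patient. The effective numbers are 300/(1 + 2 × 0.3) = 188 and 200/(1 + 0.3) = 154.

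| True rate | Comparator capture | False excess (points) | 300 v 200, independent | 300 v 200, ICC 0.3 | 95 v 95 |
|---|---|---|---|---|---|
| either | 100% | 0 | 5% | 5% | 5% |
| 14.3% | 80% | 2.9 | 15% | 12% | 9% |
| 14.3% | 70% | 4.3 | 29% | 22% | 15% |
| 20.3% | 80% | 4.1 | 20% | 16% | 11% |
| 20.3% | 70% | 6.1 | 41% | 31% | 20% |

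**Step 3. Upper bound.** If the true rate were 34.3% in both groups, under-recording alone would produce the full planned 20-point gap only at a comparator capture of 14.3/34.3 = 42%.

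**The case against.** The strongest reply is that the instrument is already shared. Section 3.3.1 has the same nurses using one scale for both drugs, and retrospective data go back only to the start of standardised recording. The medical record may simply be where the nurse's grade is stored. This largely stands, and it makes the fix cheap. It does not explain why section 4.2 says that the methods differ after enrollment.

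Some stronger readings are tempting and are not supported:

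- *Self-report or coordinator interviews inflate the ocrelizumab count.* Patient report is a separate secondary outcome (section 3.3.2), to be presented descriptively, and coordinator interviews concern additional safety issues (section 3.4). No text lets either change a nurse's Grade 0. No text rules it out either.
- *Switchers are observed longer.* Section 4.3.1 says "After completion of the infusion, the IV cannula should remain in situ for at least 1 hour". That is a safety instruction for ocrelizumab and not an endpoint window. Rituximab follows standard care, so the absence of a matching rule does not show shorter observation.
- *The pilot shows that records miss mild reactions.* Section 4.9.6 reports that "85.71% were Grade 0, 12.24% were grade 2 and 2.05% were Grade 3", with no Grade 1. The percentages fit 42, 6 and 1 of 49 patients, so only 7 reactions. If 20% of reactions were truly Grade 1, none in 7 would occur with probability 0.8^7 = 0.21; at 40% it would be 0.6^7 = 0.03. This is suggestive at most.

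It is also fair to say that the limitation is disclosed, that the study is observational, and that an excess on ocrelizumab would work against the hope in section 1 that switching brings no unexpected reactions. But the study tests for a difference and reports its size, so a distorted estimate matters in either direction.

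**Conclusion.** The concern holds as an unreconciled definition with no analysis behind it. Sections 3.3.1 and 4.2 describe ascertainment of the sole primary endpoint differently, part of the comparator data is retrospective, and nothing in section 4.9.4 addresses unequal ascertainment.

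A reader might infer that the study will show a false excess on ocrelizumab. The documents do not support that: they give neither the direction nor the size of any bias. The false-positive rates above rest on assumed comparator capture of 70% to 80%, complete capture in switchers and equal true rates. They show that moderate under-recording would be enough to matter, not that it occurs. Given the 42% bound, under-recording would more plausibly create or enlarge a modest difference than produce the planned 20 points.

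**What to change.** 1. In sections 3.3.1 and 4.9.4, define the primary IRR in both groups as the infusion nurse's recorded grade, abstracted from the infusion-centre record on one form. Apply the same counting rule to both drugs, including whether reactions noted after the infusion ends are counted. Amend section 4.2 to agree.
2. State that self-reported and coordinator-elicited reactions do not change that grade and are reported separately.
3. Pre-specify two sensitivity analyses of the primary comparison: one excluding retrospective comparator infusions, and one counting only Grade 2 or higher. Section 4.9.4 already allows grades to be dichotomised, so the second is a small addition.

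The cost is protocol and SAP wording plus one abstraction form, with no new data. Reactions captured only through the extra switching-group channels leave the primary endpoint, and the prospective-only analysis will have fewer comparator infusions. The change cannot recover reactions that were never written down, and it leaves any difference in vigilance among unblinded nurses. The limitation in section 4.2 should therefore stay, reworded to describe what remains.

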4.3 Study Treatment

Ocrelizumab will be provided free of charge by Genentech. The Sponsor Investigator of the study will ensure maintenance of complete and accurate records of the receipt, dispensation, and disposal or return of all study drug in accordance with 21 Code of Federal Regulations (C.F.R.), Part 312.57 and 312.62 and Genentech requirements. Study drug will be managed with in the UCH research pharmacy.

4.3.1 Dosage, Preparation, Administration and Storage

Ocrelizumab Formulation Packaging, and Handling

Ocrelizumab will be supplied by the Sponsor as a liquid formulation containing 30-mg/mL ocrelizumab in 20 mM sodium acetate at pH 5.3, with 4% trehalose dihydrate and 0.02% polysorbate 20. The drug product is provided as a single-use liquid formulation in a 15-cc, type I USP, glass vial fitted with a 20-mm, fluoro-resin, laminated stopper and an aluminum seal with a flip-off plastic cap and contains a nominal 300 mg ocrelizumab. No preservative is used as each vial is designed for single use.

The ocrelizumab drug product must be diluted before administration. Solutions of ocrelizumab for IV administration are prepared by dilution of the drug product into an infusion bag containing 0.9% sodium chloride to a final drug concentration of 1 to 2 mg/mL.

Ocrelizumab may contain fine translucent and/or reflective particles associated with enhanced opalescence. Do not use the solution if discolored or if the solution contains discrete foreign particulate matter. The infusion solution must be administered using an infusion set with an in-line, sterile, non-pyrogenic, low-protein-binding filter (pore size of up to 0.2 micrometer).

The prepared infusion solution of ocrelizumab is physically and chemically stable for 24 hours at 2–8°C and subsequently 8 hours at room temperature. The prepared infusion solution should be used immediately. If not used immediately, it can be stored up to 24 hours at 2–8°C. Infusion solution must be completely administered to the patient within 32 hours of preparation (not exceeding 24 hours at 2–8°C and 8 hours at room temperature). In the event an IV infusion cannot be completed the same day, the remaining solution should be discarded. For information on the formulation and handling of ocrelizumab, see the Ocrelizumab Investigator's Brochure.

Dosage, Administration, and Compliance

Ocrelizumab 600 mg will be administered as 600 mg will be administered as one 600-mg IV infusions at a scheduled interval of every 24 weeks. The first dose of ocrelizumab will be a split dose of 300 mg on day 1 and day 15 followed by 600 mg every 6 months thereafter.

Standard of care rituximab doses are 1000 mg given as first dose followed by 500mg (or 1000 mg if evidence of early B cell recovery) every 6 months thereafter. However, [The B cell depletion with rituximab can last up to two years in some patients with good efficacy demonstrated after a single dose in the HERMES study for up to a year.³](#) Patients are often out of window due to difficulties in obtaining insurance approval within the 6 month time window. Therefore, we will include those patients that receive rituximab infusions within a 12 month window.

Although ocrelizumab may be administered on an outpatient basis, patients may be hospitalized for observation at the discretion of the investigator. Ocrelizumab infusions should always be administered in a hospital or clinic environment under close supervision of the investigator or a medically qualified staff member. Each ocrelizumab infusion should be given as a slow IV infusion over approximately 150 minutes (2.5 hours) for the 300-mg dose. To reduce potential Infusion Related Reactions (IRRs), all patients will receive prophylactic treatment with 100 mg of methylprednisolone (or equivalent IV steroid), administered by slow IV infusion, to be completed approximately 30 minutes before the start of each ocrelizumab infusion.

It is also strongly recommended that the infusion is accompanied by prophylactic treatment with an analgesic/antipyretic such as acetaminophen/paracetamol (1 g) and/or an IV or oral antihistamine (such as IV diphenhydramine 50 mg or equivalent dose of alternative) 30 – 60 minutes prior to the start of an infusion to reduce potential IRRs. Patients administered a sedating antihistamine for the treatment or prevention of IRRs should be given appropriate warnings concerning drowsiness and potential impairment of ability to drive or operate machinery.

Since transient hypotension may occur during ocrelizumab infusion, the investigator may wish to withhold anti-hypertensive medications 12 hours prior to ocrelizumab infusion.

Ocrelizumab must not be administered as an IV push or bolus. Well-adjusted infusion pumps should be used to control the infusion rate, and ocrelizumab should be infused through a dedicated line. It is important not to use evacuated glass containers (to prepare the infusion), which require vented administration sets, because this causes foaming as air bubbles pass through the solution.

After completion of the infusion, the IV cannula should remain in situ for at least 1 hour to allow for administration of drugs intravenously, if necessary, in the event of a delayed reaction. If no adverse events occur during this period of time, the IV cannula may be removed and the patient may be discharged. See the Ocrelizumab Investigator's Brochure for detailed instructions on drug preparation, storage, and administration.

